### **Total sample size**

A total of 42 evaluable patients will be accrued to study.

Eleven patients will be treated in the first stage, which will assess the safety of the combination. Patients failing to complete treatment for reasons other than toxicity will be replaced.

In the second stage, 31 efficacy-evaluable patients will be enrolled, provided safety is acceptable.

### 11.2 Secondary Clinical Endpoints

Clinical secondary endpoints in phase II include adverse events, in-field and out-field, objective response rate, distant PFS, overall PFS, and overall survival.

### 11.3 Accrual

The study will be conducted at the CTRC at UTHSCSA. We anticipate that 42 evaluable patients (11 in the first stage and 31 in the second stage) will be accrued over two years, and that the monthly accrual rate will be approximately 1-2 patients per month.

### 11.4 Safety Evaluation During the Second Stage

In the phase II component of study, safety will be monitored continuously using Bayesian methods. The toxicities of the combination of RT and cetuximab have been characterized by a randomized study by Bonner et al  in which 208 patients treated with RT and cetuximab were evaluated for toxicity. Grade 3/4 radiation mucositis and radiation dermatitis were common toxicities occurring with high frequencies. The proportion of grade 3/4 events in the RT+cetuximab arm were 56% for mucositis and 23% for radiation dermatitis. While the intratumoral injection of EGFR AS is not expected to increase the rate of SAEs, we will nonetheless monitor patients for unexpected increases in mucositis and radiation dermatitis that may be attributable (possibly, probably, definitely) to the addition of EGFR AS, and will suspend the trial if there is evidence that the occurrences of these toxicities are greater than what would be expected from radiation and cetuximab without EGFR AS.

We use informative prior distributions of SAEs to conform in part to the reported SAE frequencies in Bonner – probabilities of grade 3/4 mucositis of 56% and grade 3/4 radiation dermatitis of 23%. Our assumed prior probabilities are not as concentrated as the nominal uncertainty in the

estimates from the Bonner study of 208 patients, but instead allow for greater variability, which can arise from different treatment populations. Specifically, we specify a 90% credibility interval for the probability of mucositis as 56% 15%, and 23% 10% for the probability of radiation dermatitis; these are wider intervals than suggested by the results of the study by Bonner et al.

Assuming that the prior probability of an SAE follows a beta distribution, the stopping rule is based on the updated posterior probability of an SAE. As each patient is observed for SAEs, the posterior probability, which follows a beta distribution, of SAE can be calculated. If at any time during the trial the posterior probability is  $\geq 0.80$  that the rate of treatment-related grade 3/4 mucositis exceeds 56%, the study will be suspended pending review by Data and Safety Monitoring Committee (DMSC). Similarly, if the posterior probability is greater than 0.80 that the rate of treatment-related grade 3/4 radiation dermatitis exceeds 23%, the study will be suspended for review by the DSMC. To permit continuous monitoring of SAEs, a table (see below) based on the cumulative number of patients experiencing SAEs at any point during the trial can be used to signal when the study should be suspended and reviewed by the DSMC.

**Table 6 Number of Patients Observed to Have Treatment-Related SAEs and Corresponding Posterior Probabilities Needed to Suspend the Study in Phase II**

Patients	Treatment-Related Grade 3/4 Mucositis		Treatment-Related Grade 3/4 Radiation Dermatitis	
	SAEs	Pr( $\pi \geq 0.56$ )*	SAEs	Pr ( $\pi \geq 0.23$ )
4	---	---	4	.825
5	---	---	4	.804
6	6	.814	5	.861
7	7	.848	5	.843
8	8	.877	5	.823
9	8	.832	5	.802
10	9	.862	6	.858
11	9	.815	6	.840
12	10	.848	6	.821
13	11	.875	6	.801
14	11	.833	7	.856
15	12	.862	7	.838
16	12	.818	7	.820
17	13	.848	7	.800
18	13	.803	8	.854
19	14	.834	8	.837
20	15	.862	8	.819
21	15	.821	9	.868
22	16	.849	9	.852
23	16	.807	9	.835
24	17	.837	9	.818
25	18	.863	10	.866
26	18	.824	10	.850
27	19	.851	10	.834
28	19	.811	10	.817
29	20	.839	11	.864
30	21	.864	11	.849
31	21	.827	11	.833

\*  $\pi$  is the posterior probability of a treatment-related SAE. For example, given the observed number of patients treated and the number of patients observed with SAEs, Pr( $\pi \geq 0.56$ ) is the posterior probability that treatment-related grade 3/4 mucositis exceeds 0.56, the expected value prior to study.

The table above presents the minimum number of patients experiencing treatment-related SAEs (i.e., those SAEs judged to be possibly, probably, or definitely related to the study regimen) that would dictate suspension of the trial in accordance with the stopping rule. For example, after the first 10 patients have completed treatment and been observed for toxicity, 9 patients experiencing treatment-related grade 3/4 mucositis, or 6 patients experiencing treatment-related grade 3/4 radiation dermatitis, would trigger trial suspension pending review by the DSMC.

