## 11. STATISTICAL CONSIDERATIONS

### 11.1 Primary Endpoint

This is a 2-stage clinical trial. In the first stage, toxicity will be the primary endpoint. In the second stage (phase II component), the primary endpoint will be the locoregional progression free survival (PFS) at 1 year. Toxicities will also be evaluated during the second stage using continuous Bayesian monitoring as described below.

Sample size for the primary objective: 11 evaluable patients (stage 1); 31 evaluable patients (stage 2)

First stage: 11 evaluable patients. The safety-evaluable population for stage 1 consists of all patients who either complete the treatment regimen or withdraw from study by reason of toxicity.

Toxicities due to EGFR AS in our previous phase I trial were negligible, and consisted of grade 1 injection site pain and swelling. Because we will combine EGFR AS with radiation and cetuximab in the proposed clinical trial, a separate safety evaluation will be conducted. In the first stage (safety component), 11 patients will be treated and observed for serious adverse events (SAEs) that are due to EGFR AS (possibly, probably, or definitely), not cetuximab or radiation. In the first stage, after three (3) subjects are enrolled and have received all EGFR AS injections, there will be a two-week waiting period to assess adverse events. After the two-week period, additional subjects may be enrolled. Eligible patients will include stage IV or recurrent patients who would not be eligible for the subsequent study of efficacy, and their accrual to study is only for the assessment of safety. We seek to rule out an SAE rate of 20% or greater due to EGFR AS. If no grade 3/4 toxicities due to EGFR AS are observed among 11 patients, then an upper 90% confidence bound for the SAE rate is less than 20%.

Second stage (phase II component): 31 evaluable patients. The efficacy-evaluable population consists of all patients who complete the treatment regimen.

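### The stage 2 suspension rule counts only treatment-related grade 3/4 mucositis and dermatitis against background rates that carry no attribution filter, and Section 11.4 names two different attribution targets

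*Combined protocol and SAP*

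**What the plan says.** Section 11.4 takes its benchmarks from the randomised trial of radiation with or without cetuximab: "The proportion of grade 3/4 events in the RT+cetuximab arm were 56% for mucositis and 23% for radiation dermatitis". Table 2 in Section 1.4 shows the same two figures in a table of adverse event incidence. Neither place attaches an attribution condition.

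The stated aim, "suspend the trial if there is evidence that the occurrences of these toxicities are greater than what would be expected from radiation and cetuximab", is again an unfiltered comparison. The same sentence, however, says the study will "monitor patients for unexpected increases in mucositis and radiation dermatitis that may be attributable (possibly, probably, definitely) to the addition of EGFR AS".

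The rule itself is filtered. The study is suspended when the posterior probability reaches 0.80 "that the rate of treatment-related grade 3/4 mucositis exceeds 56%, the study will be suspended", with a matching sentence for dermatitis at 23%. The title, both toxicity headings and the footnote of Table 6 carry the same qualifier, although the sentence introducing the table describes it as "based on the cumulative number of patients experiencing SAEs at any point during the trial", with no qualifier.

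The text after Table 6 defines the counted events as "those SAEs judged to be possibly, probably, or definitely related to the study regimen". Its worked example for 10 patients is "9 patients experiencing treatment-related grade 3/4 mucositis, or 6 patients experiencing treatment-related grade 3/4 radiation dermatitis".

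**The concern.** There are two linked problems. First, a filtered count is compared with an unfiltered benchmark. Removing events from the count while leaving 56% and 23% unchanged can only make suspension less likely.

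Second, the section does not settle what an event must be related to. The study regimen includes radiation and cetuximab, so almost any in-field mucositis or dermatitis would qualify. The addition of EGFR AS is a much narrower target. A team could carry the narrow reading over from stage 1, where Section 11.1 counts "serious adverse events (SAEs) that are due to EGFR AS (possibly, probably, or definitely), not cetuximab or radiation".

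Stage 2 has one arm, and this rule is the only printed comparison of these toxicities with their background rate. If the count is thinned by attribution, a real increase could go unflagged.

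**Working it through.** **Inputs.** Benchmarks of 56% and 23%, the 0.80 cut-off and the Table 6 boundaries come from Section 11.4; the 31 patients come from Section 11.1. SAE in Table 6 is read as grade 3/4, as the column headings indicate. The documents give neither the true rates under the combination nor the share of events that will be called related, so both are assumptions and are ranged.

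**Step 1: reproduce Table 6.** The posterior is Pr(π > p0 | x of n) = 1 − BetaCDF(p0; a + x, b + n − x). The beta parameters are not printed. Fitting them to the table gives about Beta(17.25, 13.64) for mucositis (90% interval 41% to 70%) and Beta(11.04, 37.01) for dermatitis (14% to 33%). These agree with the stated intervals, read as 56% ± 15 points and 23% ± 10 points.

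- Mucositis: 9/10 gives 0.862 and 21/31 gives 0.827, as printed.
- Dermatitis: 6/10 gives 0.858 and 11/31 gives 0.833, as printed.
- All printed boundaries are recovered, and the largest posterior difference is 0.0005.

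Table 6 is therefore sound as arithmetic. The question is what gets counted.

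**Step 2: probability of suspension.** Let r be the true all-cause grade 3/4 rate and s the share called related. The counted rate is p = r × s. With f(n, x) the probability of having x counted events after n patients without an earlier suspension:

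f(n, x) = f(n−1, x)(1 − p) + f(n−1, x−1) p.

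At each n, the mass at or above the Table 6 boundary is added to the suspension probability and removed. The recursion runs to n = 31, with patients independent and assessed one at a time. For example, mucositis at r = 0.76 and s = 0.95 has p = 0.722.

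**Step 3: results for a 20-point rise.**

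| Share counted | Mucositis, true 76% | Dermatitis, true 43% |
|---|---|---|
| 100% | 0.937 | 0.894 |
| 98% | 0.909 | 0.876 |
| 95% | 0.854 | 0.846 |
| 90% | 0.730 | 0.785 |
| 80% | 0.42 | 0.62 |
| 50% | 0.011 | 0.117 |

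The loss from full counting reaches 0.05 at a share of 0.967 (mucositis) and 0.948 (dermatitis). A simulation of 200,000 trials gave 0.936 and 0.909 for mucositis, and 0.895 and 0.876 for dermatitis, at shares of 100% and 98%.

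**Step 4: a 10-point rise.** At shares of 100/98/95%, mucositis (true 66%) gives 0.64/0.58/0.50 and dermatitis (true 33%) gives 0.56/0.54/0.49.

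**Step 5: the extreme EGFR AS-only case.** If only the 20-point excess itself were attributed to EGFR AS, p = 0.20 for each toxicity. Suspension probability is then about 0.0001 for mucositis and 0.08 for dermatitis.

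**Step 6: no true increase.** At a share of 100% the chance of suspension is 0.250 (mucositis) and 0.158 (dermatitis). If the two are independent, the chance of at least one is 1 − 0.750 × 0.842 = 0.368. At 98% the figures are 0.217, 0.145 and 0.330.

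**The case against.** The strongest reply is that the text after Table 6 already settles the matter. It is the only definition attached to the table's counts, and it names the study regimen. The section itself calls these events radiation toxicities, and radiation is part of the regimen, so nearly all should be at least possibly related. At a 99% share the loss is only 0.013 for mucositis and 0.009 for dermatitis.

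The earlier phrase about EGFR AS can also be read as describing the increase to be detected rather than each event to be counted. Section 11.1 shows that the authors wrote an explicit exclusion of cetuximab and radiation when they wanted one. On this view, one cross-reference would be enough.

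Other safeguards exist. EGFR AS doses are omitted or held for in-field toxicity whatever its attribution (Sections 5.2 and 7.6). Section 6.4 has quarterly review and a report to the monitoring committee for three or more of the same event. Section 6.3 has the DSMB assess adverse event trends. Suspension leads to review, not termination.

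Much of this stands. The regimen reading is the better one, the loss under it is small, and the 80% and 50% rows are not the rule's expected performance. Three things remain. The grading terms in the earlier sentence are those used for attributing individual events, so the narrow reading is open. A small loss depends on near-complete attribution: at 90% the mucositis loss is already 0.937 − 0.730 = 0.21. And none of the safeguards, as printed, compares these toxicities with the background rate.

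**Conclusion.** The concern holds, as a minor one. The count and the thresholds are on different bases, and Section 11.4 gives two attribution targets. If the definition after Table 6 is followed and at least about 97% of mucositis and 95% of dermatitis events are called related, the probability of detecting a 20-point rise falls by no more than 0.05. If staff attribute to EGFR AS alone, the rule can lose most or nearly all of its ability to detect such a rise.

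The mismatch rests on the text alone. Its size rests on the assumed shares and true rates, on independence between patients, and on assessment after each patient. How the source trial attributed its events cannot be seen from these documents; both places that quote its figures present them without a filter.

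**What to change.** In Section 11.4, count every grade 3/4 mucositis and radiation dermatitis regardless of attribution:

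- In the sentence on monitoring for unexpected increases, replace the clause on attribution to EGFR AS with a statement that events are counted regardless of attribution.
- Delete the qualifier *treatment-related* from the two threshold sentences, the Table 6 title, its two toxicity headings and both places in its footnote.
- In the paragraph after Table 6, delete the qualifier in all three places, together with the parenthesis defining relatedness.
- Keep the printed boundaries, the grade 3/4 definition and the denominator. Attribution is still recorded and reported under Section 11.6, Safety Profile.
- State beside the rule that, with no true increase, the chance of suspension for review is 0.25 for mucositis and 0.16 for dermatitis.

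The cost is text edits only, with no new data. Compared with a 98% share, full counting raises the chance of an unneeded suspension by about 0.03 for mucositis (0.217 to 0.250) and 0.01 for dermatitis (0.145 to 0.158). For at least one of the two it rises from 0.33 to 0.37, assuming independence.

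A lighter edit would point the earlier sentence to the regimen definition. That removes the ambiguity but still compares a filtered count with unfiltered thresholds.

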### 11.5 Hypothesis Testing and Operating Characteristics for Correlative-Study Endpoints

Correlative studies will assess antitumor activity measured by levels of biomarker expression. This will involve measurement of the following biomarkers from tumor tissue using RPPA: EGFR, pEGFR, Src, pMAPK, STAT3, pSTAT3, pSTAT5, pSTAT1, pAKT, p38, p21, p27, PARP, E-cadherin, p-ErbB3, and Ki67. In some instances immunohistochemical staining of selected proteins will be performed to verify or validate RPPA results. Biomarkers will be tested for treatment-associated modulation (i.e., change from baseline) as well as for association with 1-year locoregional PFS (primary endpoint), and other efficacy parameters, such as objective response rate, PFS, and overall survival. These analyses will be exploratory in nature.

To estimate the power of our study to assess whether significant modulation of biomarkers occurs from therapy, we assume that 80% of patients in phase II will have a 2nd biopsy after 2 doses of cetuximab with EGFR AS, thereby providing paired tumor tissue samples in 24 patients total. Based on data from a prior phase I clinical trial, the standard deviation was 0.7 on average for paired differences ( $\log_2[\text{post}/\text{baseline}]$ ) in proteins measured pre and post therapy. Assuming this standard deviation will apply, a two-tailed signed rank test at  $\alpha = 0.01$  (to control the false-positive rate) in 24 patients will provide 80% power to detect a change of 0.55 ( $\log_2$  scale), which corresponds to a change of ~46% from the baseline-expression level. Although the search for individual biomarkers that change with treatment is exploratory and hypothesis generating, we will report all nominal p-values along with those that remain significant using a 10% false discovery rate.

It is also of interest to assess whether biomarker modulation within the treatment window is associated with PFS. To estimate power for these analyses, we use Cox proportional hazards regression to evaluate whether PFS depends on change in biomarker expression, considered for each biomarker individually. We assume that 25% of treated patients will have loco-regional progression within 1 year, i.e., PFS = 0.75, based on expectation averaged over the null and alternative hypotheses. We also assume that among 31 patients enrolled in phase II, 24 will have adequate tissue and biomarker assessments before and after therapy. We further assume that accrual in phase II will take 18 months, with 12 months of follow-up beyond the last patient enrolled. Under exponential survival, these assumptions imply that 9 of the 24 patients with pre-post biomarker measurements will have loco-regional progression within our study time frame. A two-tailed Cox-regression test of trend at  $\alpha = .05$  will therefore have 80% power to detect a hazard ratio of 3.8, which corresponds to a one-unit change (i.e., 2-fold increase or decrease) in the biomarker tested.

With respect to assessing PFS in relation to baseline measurements of biomarkers, we assume that all 31 patients enrolled in study will have tissue available for analysis, in which case 12 patients are expected to have loco-regional progression within the study time frame. For this

situation, the minimum detectable hazard ratio would be 3.2 under the conservative assumption that variability in biomarker expression among patients is no greater than that within patients (greater variability would provide increased opportunity to detect biomarker effects).

The analyses of the correlative data are exploratory. A less restrictive test ( $\alpha = .05$ ) is used for PFS to avoid missing important leads. Nominal p-values for all biomarkers associated positively or negatively with PFS will be reported along with a designation of those that fall within a 10% false discovery rate.

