### **STUDY SCHEMA**

Radiation once daily, 200 cGy/day, 5 days/week x 7 weeks, to 70 Gy

- Cetuximab 400 mg/m^2 IV day, loading dose 2 weeks prior to starting RT  
 Cetuximab 250 mg/m^2 IV weekly, 1 week prior to and during radiation (until radiation completion)
- Intratumoral EGFR AS injections weekly until no identifiable tumor or to a maximum of 7 weeks, starting 2 weeks prior to radiation, after the initiation of cetuximab. The same lesion (primary tumor or lymph node), which will be the dominant and more accessible tumor, will be injected during treatment with EGFR AS.
- Tumor biopsies will be performed prior and after 2 weeks of cetuximab plus EGFR AS (prior to starting radiation).

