### 1.4 Cetuximab

Cetuximab binds specifically to the EGFR on both normal and tumor cells, and competitively inhibits the binding of epidermal growth factor and other ligands, such as transforming growth factor- $\alpha$ . Binding of cetuximab to the EGFR blocks phosphorylation and activation of receptor-associated kinases, resulting in inhibition of cell growth, induction of apoptosis, and decreased matrix metalloproteinase and vascular endothelial growth factor production. The EGFR is constitutively expressed in many normal epithelial tissues, including the skin and hair follicle.

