## 2. OBJECTIVES

- To evaluate the safety of the combination of intratumoral EGFR AS DNA with standard cetuximab and radiation.
- To evaluate the locoregional control (primary endpoint), in patients with locally advanced SCCHN treated with intratumoral EGFR antisense DNA combined with standard radiation plus cetuximab.
- To evaluate the toxicities associated with the above treatment.
- To evaluate other efficacy parameters, including the objective response rate, distant control and overall progression-free survival, and overall survival.
- To determine the effect of EGFR antisense therapy on EGFR and EGFR-related biomarkers. We will use reverse phase protein microarrays (RPPA) and immunohistochemical (IHC) analysis of tissue microarrays (TMA), on baseline and post-treatment tumor tissue, to determine the expression level and modulation of a panel of EGFR and EGFR-pathway related biomarkers, including (but not necessarily limited to) EGFR, pEGFR, Src, pMAPK, STAT3, pSTAT3, pSTAT5, pSTAT1, pAKT, p38, p21, p27, PARP, E-cadherin, p-ErbB3, and Ki67. We hypothesize that the baseline expression or modulation of one or more EGFR signaling proteins will correlate with objective response rate and locoregional control after combined modality treatment.
- To examine the transfection of the EGFR antisense gene therapy in vivo.

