outpatient setting, at the time or after the second dose of EGFR AS and after the second cetuximab dose, in addition to the pretreatment biopsy. Therefore, the tumor will be biopsied 2 times. When possible, we will biopsy adjacent areas of the tumor at each time point to determine heterogeneity of transfection and EGFR expression. When possible, additional biopsies will be obtained from non-injected areas that are more than 2 cm apart from an injection site. A comparison of biopsies from injected and non-injected lesions will provide the opportunity to assess the added effect of EGFR AS. Prior injection sites will be marked and attempts will be made to perform biopsies in the area of prior inoculation(s). Biopsies will be delivered to [name]'s laboratory at CTRC and to [name] laboratory at UPCI for molecular studies. The presence of EGFR antisense DNA in the tumors will be determined using PCR. EGFR and EGFR pathway will be evaluated using RPPAs and IHC (see correlative studies section).

[name] or  
[name].  
Co-Director, Preclinical Research  
CTRC Institute for Drug Development  
Assistant Professor  
Department of Medicine/Division of Hematology and Medical Oncology  
University of Texas Health Science Center at San Antonio  
[name]  
[name]  
[name]  
[contact]  
Email: [contact]  
Email: [contact]

[name]  
University of Pittsburgh  
Head and Neck Cancer Signaling Laboratory  
[name]  
[name]  
[contact]  
Email: [contact]

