Sample size for the second stage of study is based on the primary endpoint: 1-year locoregional PFS. We use a historical control rate of 63% for 1-year locoregional PFS in patients on radiation and cetuximab, as reported by Bonner et al. To account for the inherent variability in this estimate, and to improve the likelihood that we can detect a true improvement with the addition of EGFR AS, we use the reasoning of Fazzari et al. which advocates setting the null hypothesis to the upper bound of the 75 percent confidence interval for the historical-control endpoint. By assuming that 1-year locoregional PFS as reported by Bonner et al follows an exponential distribution from a

sample of 211 patients, the upper 75th percent confidence bound for 1-year locoregional PFS is 68%. Targeting a 50% reduction in the hazard rate for 1-year locoregional PFS under our treatment regimen implies that 1-year locoregional PFS would be improved to 83%. To achieve this objective, we plan a study with 2 years of patient accrual, 1 year of additional follow-up, and assume that 1-year locoregional PFS will have an exponential distribution. Under these assumptions, a 1-sided exponential test at  $\alpha = 0.10$  will provide 90% power with 31 patients. In addition, we plan to evaluate tumor response and locoregional progression in injected and non-injected lymph nodes. The rates of progression in injected versus non-injected regions will be compared by an exact test for two rates, implemented in StatXact 8.

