To date, over 100 monospecific antibodies have been validated for use in RPPA (see <http://home.ccr.cancer.gov/ncifdaproteomics>). MDACC and NCI/FDA maintain a joint database of validated antibodies for RPPA. These antibodies detect a variety of proteins involved in phosphorylation, apoptosis (activated and cleaved proteins) and cell cycle progression (cyclins, phosphohistones p21, p27). Although up to 100 antibodies have been validated, we will prioritize pathways and antibodies for analysis. Blockade of EGFR in head and neck cancer cell lines leads to downregulation of several downstream signaling proteins including pSrc, pMAPK, pSTAT3, pSTAT5, pSTAT1, and pAKT. The first tier of proteins/phosphoproteins would include EGFR, pEGFR, Src, pMAPK, STAT3, pSTAT3, pSTAT5, pSTAT1, pAKT, p38, p21, p27, PARP, E-cadherin, p-ErbB3, and Ki67. Additional pathways/proteins can be evaluated as other antisera are validated and/or new hypotheses emerge from ongoing experiments.

Frozen tumor will be homogenized with lysis buffer. Lysates will be boiled with 1% SDS, mimicking the stringent conditions used in immunoblotting. After centrifuging, the protein-rich supernatant can be stored at  $-80^{\circ}\text{C}$  and transferred to the [name] laboratory at MDACC for RPPA. The cost of setting up a RPPA facility (~\$500,000) requires that the lysates be arrayed in the [name] lab. Serial dilutions with additional lysis buffer are generated from each lysate immediately prior to array preparation using a Tecan liquid handling robot. A robotic arrayer then creates a 640 spot array on nitrocellulose-coated glass slides where each spot on the array represents a precise dilution of a particular sample lysate. As many as 160 different samples with 4 serial dilutions can be studied on a single slide and with robotics, 24 identical slides can be printed at a time. The [name] lab has successfully transferred lysates from center to center with retention of signals. Each slide is then probed with a specific validated primary antibody under optimal blocking conditions to minimize

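### The change-from-baseline biomarker test in section 11.5 measures cetuximab and EGFR AS together; the injected versus non-injected comparison that bears on EGFR AS alone is not in the analysis plan

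*Combined protocol and SAP*

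**What the plan says.** The correlative objective in section 2 is "To determine the effect of EGFR antisense therapy on EGFR and EGFR-related biomarkers". The research abstract has the same objective.

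The study schema fixes the biopsy times: "Tumor biopsies will be performed prior and after 2 weeks of cetuximab plus EGFR AS (prior to starting radiation"). Section 5 places the first biopsy before cetuximab starts.

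Section 11.5 gives the test: "Biomarkers will be tested for treatment-associated modulation (i.e., change from baseline"). It is a two-tailed signed rank test at alpha 0.01 on 24 pairs, with an SD of 0.7 for the log2 differences and 80% power for a change of 0.55. The section calls the work exploratory and applies a 10% false discovery rate.

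Two background statements bear on how the result can be read. Section 1.4 says of cetuximab: "Binding of cetuximab to the EGFR blocks phosphorylation and activation of receptor-associated kinases". Section 13.1 says: "Blockade of EGFR in head and neck cancer cell lines leads to downregulation of several downstream signaling proteins".

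Section 5.2 recognises the need for another contrast. It says "When possible, additional biopsies will be obtained from non-injected areas that are more than 2 cm apart from an injection site", and then "A comparison of biopsies from injected and non-injected lesions will provide the opportunity to assess the added effect of EGFR AS". Sections 11.5, 11.6 and 13 give no test, expected number or power for that biomarker comparison, and Table 7 lists no non-injected specimen. The one injected versus non-injected test that is specified, in section 11.1, concerns another outcome: "The rates of progression in injected versus non-injected regions will be compared by an exact test for two rates".

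**The concern.** Both drugs start between the two biopsies and both act on EGFR. There is no cetuximab-only arm and no scheduled biopsy between the start of cetuximab and the start of EGFR AS. A change from baseline is therefore a change under the combination, whereas the objective asks about one component.

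Section 13.1 names six phosphoproteins that fall when EGFR is blocked. Five of them (pMAPK, pSTAT3, pSTAT5, pSTAT1 and pAKT) are in the panel tested under 11.5. Cetuximab could plausibly move them without any contribution from EGFR AS.

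What is at stake is interpretation. The plan pairs an objective about antisense with a test that cannot separate antisense from cetuximab, and leaves undefined the one comparison that might. Either the objective goes unanswered, or the pre-post result is taken to answer it.

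**Working it through.** **Inputs.** From section 11.5: 24 pairs (80% of 31 = 24.8, taken as 24), SD 0.7 on the log2 scale, two-sided alpha 0.01, change 0.55. Not in the documents, and therefore assumed: the size of any cetuximab-only shift, the number of patients with a non-injected biopsy, and the SD of the injected versus non-injected contrast.

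**1. The plan's own figure.** Approximate the signed rank test by a t test with effective sample size n_e = n × 3/π = 24 × 0.955 = 22.9. The noncentrality is 0.55 × √22.9 / 0.7 = 3.76, and the noncentral t gives 81.5% power. Simulation of normal differences with the exact signed rank critical value (attained size 0.0096) gives 82%. The stated 80% is reproduced. The back-transformation also holds: 2^0.55 = 1.46, a 46% increase.

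**2. What the test estimates.** Let C be the mean log2 change due to cetuximab and A the change added by EGFR AS. The mean pre-post change is C + A, and the test addresses C + A = 0. Setting A = 0 shows how it responds to cetuximab alone:

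| Assumed cetuximab-only shift (log2) | Probability of a significant result |
|---|---|
| 0 | 1% |
| 0.25 | 16% |
| 0.40 | 49% |
| 0.55 | 82% |
| 0.70 | 97% |

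Neither alpha 0.01 nor the 10% false discovery rate changes this. Both control chance findings; neither says which drug caused a real change.

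**3. What an injected versus non-injected contrast estimates.** Suppose that cetuximab, given intravenously, has the same mean effect at both sites. Let S be any EGFR AS effect that reaches the non-injected site. The difference between sites in change from baseline then has mean (C + A) − (C + S) = A − S. The week-2 ratio log2(injected/non-injected) has mean B + A − S, where B is any difference between the sites before treatment. The difference in changes removes B; the week-2 ratio does not.

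**4. Precision of that contrast.** Same test, two-sided alpha 0.01. An SD of 0.7 carries over the plan's value. An SD of 0.99 = 0.7 × √2 is that of the difference between two uncorrelated changes, each with SD 0.7. Figures are the effects (log2) detectable with 80% power:

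| Pairs | SD 0.7 | SD 0.99 |
|---|---|---|
| 24 | 0.54 | 0.76 |
| 18 | 0.64 | 0.91 |
| 12 | 0.84 | 1.19 |
| 8 | 1.34 | 1.90 |

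The rows for 18 and 12 pairs use the approximation in step 1; those for 24 and 8 are simulated with the exact critical value. Simulated power for an added effect of 0.55 is 37% with 12 pairs at SD 0.7, 16% with 12 pairs at SD 0.99, and 6% with 8 pairs at SD 0.99.

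**The case against.** The strongest reply is that section 11.5 never attributes the pre-post change to EGFR AS. It speaks of modulation associated with treatment and says that the second biopsy follows cetuximab with EGFR AS. A reader might infer that the plan would report a cetuximab effect as an antisense effect. The documents do not say so, and that inference should not be pressed. What stands is narrower: the objective names antisense, and no test in the analysis plan addresses it.

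A second reply is that section 5.2 already names the right comparison. It does, so the authors saw the problem. But it offers the comparison as an opportunity, without a test, an expected number of pairs or a place in section 11.

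A reader might also infer that non-injected biopsies are assured and would isolate the antisense effect. The documents do not support that either:

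- The biopsies are taken only when possible, and neither Table 7 nor the study parameters table lists them.
- The injected lesion is chosen as the dominant and most accessible one (section 5.2), so it may differ from non-injected tissue before treatment. Section 5.2 does not clearly provide a non-injected baseline sample.
- Appendix III reports plasmid DNA outside the injected muscle in mice, and tumor inhibition after intravenous dosing, so spillover is possible.

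These objections limit what the contrast can show and rule out relying on a week-2 ratio alone where baseline tissue exists at both sites. They do not make the pre-post test an answer to the antisense objective.

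Finally, the analyses are exploratory, and the primary endpoint, sample size and safety monitoring are untouched. That is right, and it sets the severity.

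**Conclusion.** The point holds as a mismatch between objective and analysis. The only modulation test in 11.5 estimates the joint effect of cetuximab and EGFR AS, so it cannot by itself determine the effect of EGFR antisense therapy. The comparison described for that purpose in section 5.2 was not carried into the analysis plan and depends on biopsies taken only when possible.

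The plan's power calculation is sound for the contrast that it tests. The 82% figure is that same power with the whole effect assigned to cetuximab. It shows that a significant result need not involve EGFR AS; it does not predict how large cetuximab's effect will be. The precision figures for the alternative contrast rest on assumed SDs of 0.7 and 0.99 and assumed numbers of pairs, and reading that contrast as an EGFR AS effect further assumes similar cetuximab effects at both sites and little spillover.

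Severity is minor.

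**What to change.** In section 11.5:

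1. State that the pre-post change is the combined effect of cetuximab plus EGFR AS and is not evidence of an EGFR AS effect alone.
2. Add, as the exploratory analysis for the antisense objective, a paired within-patient injected versus non-injected comparison by signed rank test, with an estimate and confidence interval. Use the difference in change from baseline where both sites have baseline tissue, and otherwise the week-2 log2 ratio. Report the number of pairs, separately for the two forms.
3. State the limits: an opportunistic subset, differences between lesions, possible spillover, and low precision.

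Listing the non-injected specimen in Table 7 would keep the two sections consistent.

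The cost is wording and a small additional analysis; no biopsies beyond those described in section 5.2 are needed. The drawback is that the added comparison may be too imprecise to show a moderate effect, which is why the estimate, interval and number of pairs matter more than the p-value. The relabelling in item 1 is worth making even if very few non-injected samples are obtained.
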